Cryopreserved amniotic membrane (AM) is designated as human cell and tissue-based product (HCT/P) by the U.S. Food and Drug Administration (FDA) when used in ocular surface reconstruction through Request for Designation in 2001. It is minimally manipulated and considered homologous when used to repair ocular surface damage.⁸ The effectiveness of AM has been credited to its anti-inflammatory, anti-scarring, and anti-angiogenic effects. PROKERA® is a Class II medical device comprised of AM fastened in between a ring system and has been cleared by the FDA to cover the corneal surface without sutures via 510(k) #K032104 and is intended for use in eyes, in which the ocular surface cells have been damaged or underlying stroma is inflamed and scarred.⁹ Clinical uses of both AM and PROKERA® in ophthalmology have been regarded as a standard of care in the United States and is supported by three Level I CPT Codes (65778 and 65779 for AM and 65780 for PROKERA®) issued by the American Medical Association and reimbursed by the Centers of Medicare and Medicaid Services (CMS). The clinical effectiveness of both AM and PROKERA® in managing a variety of ocular surface disorders have been supported by several hundred peer-reviewed scientific publications.¹⁰

Among the ocular surface disorders managed by the device, PROKERA® has been used to manage ocular signs and symptoms of DED. In a retrospective study by Cheng et al,¹⁰ PROKERA® was placed for 5 days (Range: 2-8 days) in 15 eyes of 10 patients with moderate to severe DED. The dry eye severity ranged from Grade 1 to 4 according to the Report of the International Dry Eye Work Shop (DEWS) 2007.¹ All patients experienced symptomatic relief for a mean period of 4.2 months (Range: 0.3-6.8). Such improvement was accompanied by reduction of Ocular Surface Disease Index (OSDI) symptom scores, the use of topical medications, conjunctival hyperemia, and corneal staining as well as improvement in the quality of vision.¹¹ In a single site prospective, randomized, and controlled study conducted by John et al¹², PROKERA® together with standard of care was placed in 10 patients for 3.4 ± 0.7 day (Range: 3-5 days) while standard of care was instituted in another 10 patients as the control. All 20 patients presented with moderate to severe DED with DEWS Grade 2-4. Compared to the control arm of 10 patients receiving standard of care, the treatment arm of 10 patients receiving PROKERA® together with standard of care resulted in reduction of symptoms based on SPEED

CLINICAL STUDY PROTOCOL

score and signs such as superficial punctate keratitis (SPK) measured by fluorescein staining, leading to an overall reduction of the mean DEWS severity score from 2.9 ± 0.3 at baseline to 1.1 ± 0.3 at 1 month and 1.0 ± 0.0 at 3 months, respectively (both $p \leq 0.001$). These palliative benefits are correlated with an increase of corneal nerve density measured by *in vivo* confocal microscopy from $12,241 \pm 5,083 \mu\text{m}/\text{mm}^2$ at baseline to $16,364 \pm 3,734 \mu\text{m}/\text{mm}^2$ at 1 month, and $18,827 \pm 5,453 \mu\text{m}/\text{mm}^2$ at 3 months (both $p=0.015$). The increase of corneal nerve density is also correlated with an increase of corneal sensitivity measured by a monofilament in the Bonnet-Crochet esthesiometer. A lasting benefit for more than 3 months after one placement of PROKERA® was also demonstrated in a retrospective study by McDonald et al¹³ in 97 eyes of 84 of patients with moderate to severe DED (DEWS 2-4), of which the majority presented with symptoms of ocular discomfort, blurry vision, ocular pain, redness, and light sensitivity. Most of the cases manifested the ocular sign of SPK due to exposure keratitis, filamentary keratitis, epithelial defect, and neurotrophic keratitis. A single placement of PROKERA® for 5.4 ± 2.8 days leads to notable improvement of DED symptoms and reduction of ocular signs in 74 subjects (88%) as evidenced by notable reduction of the mean DEWS severity score from 3.25 to 1.44 at 1 week, 1.45 at 1 month, and 1.47 at 3 months. Collectively, these data suggest that a single placement of PROKERA® is effective in reducing signs and symptoms of DED for a period lasting at least three months, presumably through a number of mechanisms known for AM including anti-inflammation as well as the resultant benefit to promote the return of corneal nerve density and corneal sensitivity, which has been reported to decline as DED increases its severity.¹²

The present study is designed to further substantiate the effectiveness of PROKERA® in reducing signs and symptoms of DED.

STUDY OBJECTIVES

The primary objective is to evaluate the safety and effectiveness of PROKERA® in reducing signs and symptoms of dry eye disease (DED).

STUDY DESIGN:

We propose to conduct a prospective randomized, and controlled study to compare the effectiveness of PROKERA® plus standard of care (SOC) in the PROKERA® Arm to SOC alone in the Control Arm. Subjects presenting with moderate DED defined as corneal fluorescein staining score of ≥ 3 points out of 9,¹⁴ will be recruited and screened at the two to three participating clinical site(s) in the United States.

Following a run-in period of 2 weeks during which enrolled subjects will use standard dry eye therapies consistent with what is described in the 2007 Report of the International Dry Eye WorkShop (DEWS)^{1,15} [e.g. preservative-free artificial tears, Restasis® (0.05% Cyclosporine A, Allergan, Inc. Irvine, CA), Xiidra® (5% lifitegrast ophthalmic solution, Shire, Lexington, MA), punctal occlusion, etc.], enrolled subjects who still present with signs and symptoms of moderate

[figure not shown]
CLINICAL STUDY PROTOCOL

DED at the screening visit, will continue in the study. Those subjects whose signs and symptoms abate during the run-in period will be discontinued from the study. Subjects who continue in the study will be assigned an appropriate study identification code, and randomized to receive either PROKERA plus SOC or SOC alone.

Subjects assigned to PROKERA plus SOC will have PROKERA inserted into one eye (study eye) and will then restart the SOC treatment for both eyes after randomization. After the PROKERA application for 5 ± 1 days together with SOC, all subjects in the PROKERA® Arm will return to the clinic to have the PROKERA removed and will continue with the SOC treatment for both eyes. Subjects assigned to the Control Arm will start the SOC treatment for both eyes after randomization and will not return to the clinic at 5-day visit. Clinical symptoms will be evaluated by OSDI scale¹⁶ and the Eye Dryness Score (EDS).^{17,18} Signs of corneal epithelial damage will be evaluated by corneal fluorescein staining at the baseline, one month, two months and three months. To assess the potential for a contralateral effect, the above evaluation will also be conducted, for the subject's fellow eye (i.e. non-study eye). In order to eliminate bias, all evaluators will be masked as to the treatment assignment.

STUDY SUBJECTS AND RANDOMIZATION:

Subjects will first be randomized in a 1:1 ratio to either PROKERA® Arm (i.e., PROKERA plus SOC) or Control Arm (i.e., SOC only) by a computer-generated randomization code. For the PROKERA® Arm, one eye of each subject will be randomly assigned as the primary study eye.

CLINICAL STUDY PROTOCOL
STUDY FLOWCHART:

STUDY PRODUCT AND MODE OF ADMINISTRATION:

PROKERA® is manufactured by TissueTech, Inc. (Miami, FL), and is distributed by BioTissue, Inc., which is a solely owned subsidiary of TissueTech, Inc. PROKERA® is a corneal-epithelial insert, consisting of an ophthalmic conformer that incorporates cryopreserved amniotic membrane. PROKERA® is a Class II medical device that was cleared by the FDA under 510(k) #K032104 with the intended use in eyes in which the ocular surface cells have been damaged, or underlying stroma is inflamed and scarred.

Following the evaluations performed at the baseline visit, PROKERA®(Slim) will be inserted in the subject's primary study eye between the ocular surface and the eyelid as follows:

1. Apply topical anesthesia
2. Hold the upper eyelid

CLINICAL STUDY PROTOCOL

3. Ask the subject to look down
4. Insert the PROKERA® into the superior fornix
5. Pull lower eyelid down and slide PROKERA® under the lower eyelid
6. Check centration under the slit lamp
7. Apply a tape-tarsorrhaphy over the lid crease (standardized/specified in the full study protocol).

STUDY POPULATION/ DURATION:

A minimum of 50 subjects with moderate DED will be enrolled and randomized in this study. Following the baseline visit at which the subject will be randomized to either PROKERA® Arm or the Control Arm, one of the two eyes will be designated as the primary study eye. Each subject will be evaluated for a period of three months.

PARTICIPANTS' ELIGIBILITY:
Inclusion Criteria

- Subjects with moderate dry eye defined as corneal fluorescein staining score of ≥ 3
- Age ≥ 18 years
- Distance best corrected visual acuity better than 20/60 Snellen equivalent in each eye
- Willing to sign a written informed consent to participate
- Able to follow study instructions, with the intention of completing all required visits

Exclusion Criteria

- Presence of persistent corneal epithelial defect or ulcer in either eye
- Presence of active ocular infection in either eye
- Presence of ocular inflammation that is not related to keratoconjunctivitis sicca, e.g., allergy, severe blepharitis
- Presence of other corneal disorder(s) that give rise to reduced corneal sensitivity, such as recurrent herpes keratitis
- Presence of corneal diseases other than dry eye that can disturb the pre-corneal tear film such as epithelial basement membrane dystrophy (EBMD)
- Contact lens wear
- History of recent ocular surgery/trauma, which could affect corneal sensitivity, e.g., corneal transplantation, LASIK
- Presence of cicatricial ocular surface diseases
- A medical or ocular condition, or a personal situation, which in the principal investigator's opinion, is not appropriate for participation in the trial

CLINICAL STUDY PROTOCOL

- Any scheduled or planned ocular or systemic surgery or procedure during the study
- Pregnancy and women who are expecting to be pregnant.
- Current enrolment in another interventional drug or device study or participation in such a study within 30 days of anticipated entry into this study

ENDPOINTS/ OUTCOME MEASURES:
1) EFFECTIVENESS ASSESSMENTS:
Primary Effectiveness Endpoint:

The primary effectiveness endpoint will be defined as the difference in mean change of the total corneal fluorescein staining score of the primary study eye from baseline to 1 month.

Secondary Effectiveness Endpoints

The secondary effectiveness endpoint will be defined as:

- The difference in mean change of the EDS score from baseline to 1 month.
- The difference in mean change of the OSDI score from baseline to 1 month.

Exploratory Outcomes:

- The mean changes of the corneal fluorescein staining score of the primary study eye from baseline at 2 months and 3 months.
- The mean change of the EDS score from baseline at 1 week, 2 months and 3 months.
- The mean change of the OSDI score from baseline at 1 week 2 months and 3 months.
- The same analyses at each time point for the study eye will also be conducted for the subject's fellow eye (i.e. non-study eye)

The Dry eye sign of each eye will be evaluated by the degree of corneal fluorescein staining score. The corneal fluorescein staining score is the sum of three scores by subdividing the entire cornea into upper 1/3, middle 1/3, and lower 1/3, of which each will be graded from 0 (no staining) to 3 (diffuse staining). Thus, corneal fluorescein staining score ranges from 0 to 9, with higher scores representing more severity.

Dry eye symptoms will be evaluated using the EDS visual analog scale (VAS) to provide a direct assessment of the subject's perception of their current eye dryness symptoms. The VAS has frequently been used for the collection of patient-reported outcomes and has been

CLINICAL STUDY PROTOCOL

commonly used to assess dry eye symptoms in clinical studies. As such, the 2007 report of the International Dry Eye Workshop (DEWS) listed the VAS as a well-defined symptom assessment methodology suitable for use in dry eye clinical trials. Specifically, patient-reported outcomes assessed using the EDS (via VAS) have been used in other dry eye studies and were recently used as the primary symptom endpoint for FDA approval of lifitegrast (Xiidra) for the treatment of the signs and symptoms of dry eye disease.

The Dry eye symptoms will also be evaluated using the validated, 12-item Ocular Surface Disease Index (OSDI) (Allergan, Inc., Irvine, CA), which assesses symptoms of ocular discomfort, effects on visual function, and the impact of environmental triggers. The 12 items are graded on a scale of 0 to 4, where 0 indicates none of the time; 1, some of the time; 2, half of the time; 3, most of the time; and 4, all of the time. The total OSDI score is then calculated on the basis of the following formula: OSDI= [(sum of scores for all questions answered) \times 100]/ [(total number of questions answered) \times 4]. Thus, the OSDI is scored on a scale of 0 to 100, with higher scores representing greater disability.

2) SAFETY ASSESSMENTS:

Adverse events (AEs) during this study are expected to have the same probability of occurrence and of the same magnitude as would be found with subjects with DED and not participating in the study. These could include worsening of the signs and symptoms of dry eye. Some adverse events might be related to PROKERA® placement (adverse device effects -ADEs) which include PROKERA® intolerance, eye irritation, lid swelling and mucus discharge. However, these device related risks are no different in type or frequency when the device is used for dry eye as compared to use of the device for other ocular surface disorders which are already on-label under the FDA 510(k) clearance.

Safety will be assessed by documenting ADEs, in which the severity, cause and the resolution will be evaluated and reported. The Investigators will determine the severity, assign attribution, and report the event according to the Protocol guidelines. Serious ADEs such as vision threatening conditions may indicate patient withdrawal or termination of the study.

STATISTICAL METHODS:

The primary effectiveness analysis will be conducted on the primary effectiveness measure, the corneal fluorescein staining score change from baseline of the primary study eye, using a mixed-effects model of repeated measures (MMRM) for all randomized eyes within the intent-to-treat (ITT) population, with 1 month being defined as the primary effectiveness endpoint. The MMRM model will utilize Statistical Analysis System's (SAS) PROC MIXED program to perform this analysis and define treatment (PROKERA plus SOC vs. SOC) at 1 month and

CLINICAL STUDY PROTOCOL

treatment-by-month as fixed effects and subject as random effect as well as the baseline corneal fluorescein staining score of the primary study eye as the covariate. The effect of month includes 3 assessments at 1 month, 2 months, and 3 months. The comparison between PROKERA plus SOC and SOC at each month will be conducted, using a model-based t-test procedure, at the significance level of 0.05 (2-sided). The comparison between PROKERA plus SOC and SOC at 1 month will be defined as the primary effectiveness endpoint, whereas the comparisons at 2 months and 3 months will be exploratory analyses.

The OSDI total score change of the primary study eye from baseline over 3 months of the treatment assessment will be analyzed using the same MMRM model described above for the primary effectiveness measure. The comparison between PROKERA plus SOC and SOC at 1 month will be defined as the secondary effectiveness endpoint whereas the comparisons at 1 week, 2 months and 3 months will be exploratory analyses.

To assess the potential for a contralateral eye effect, the above analyses will also be conducted, the subject's fellow eye (i.e. non-study eye) as another exploratory outcome.

SAMPLE SIZE CALCULATION

The sample size is estimated according to the outcomes reported by John et al.¹¹ The mean corneal fluorescein staining score does not change in the control group (2.8 at baseline and 2.9 at 3 months) while PROKERA® group reduces the corneal staining from the mean grading score of 2.8 at baseline to 0.8 (SD=0.4) at 1 month and 0.6 (SD=0.5) at 3 months in patients with moderate to severe DED. This result yields a reduction of more than 70% or an effect size of more than 2.0 over 3 months from baseline.

Assuming a large effect size of at least 0.85 for the PROKERA® Arm (i.e., PROKERA® plus SOC) against the Control Arm (i.e., SOC only) at 1 month from baseline for the corneal fluorescein staining score, 23 subjects per group or 46 subjects in total are needed to be randomized to yield an 90% power at a 2-tailed significance level of 0.05, using two-sample t-test, to detect such a difference between the two treatments. The effect size of 1.00 is equivalent to a reduction of approximately 35% in corneal fluorescein staining score from baseline for the PROKERA® Arm compared to the Control Arm. To further account for an around 10% dropout, the study plans to enroll and randomize 50 subjects in total.

CLINICAL STUDY PROTOCOL
REFERENCES

1. The definition and classification of dry eye disease: report of the Definition and Classification Subcommittee of the International Dry Eye WorkShop (2007). *Ocul Surf*. 2007; 5: 75-92.
5. Bron AJ, de Paiva CS, Chauhan SK, et al. TFOS DEWS II pathophysiology report. *Ocul Surf*. 2017; 15: 438-510.

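### With two to three sites, the plan states no site stratification or blocking, and the listed primary model has no site term: a cheap, modest gain in balance and precision is left unused.

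*Combined protocol and SAP*

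**What the plan says.** Study Design states that subjects "will be recruited and screened at the two to three participating clinical site(s) in the United States". The allocation method is given in Study Subjects and Randomization: "Subjects will first be randomized in a 1:1 ratio to either PROKERA® Arm" or the Control Arm, "by a computer-generated randomization code". No stratification factor, block size or site-specific list is mentioned.

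Statistical Methods lists the terms of the primary repeated-measures model: treatment, "treatment-by-month as fixed effects and subject as random effect as well as the baseline corneal fluorescein staining score of the primary study eye" as covariate. Site is not among them. The same model is carried over to OSDI. The documents contain no site-adjusted sensitivity analysis and no treatment-by-site check.

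Three further facts bear on whether site matters:

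- Endpoints/Outcome Measures defines the primary outcome as the sum of three corneal-zone grades, each from 0 to 3. No central reading or grader calibration is described.
- Study Design gives SOC as an open list of examples. It does not say who selects the therapy or whether it is the same across sites.
- Study Design also states that all evaluators are masked to treatment assignment.

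**The concern.** In a trial of 50, each site contributes perhaps 17 to 25 subjects, and fewer if recruitment is uneven. Grades assigned by eye and SOC that is not standardised could both make outcomes differ between sites. If so, two things follow. An allocation not balanced within site lets part of the site difference fall into the treatment contrast by chance. A model without site also leaves between-site variance in the error term.

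The study has little precision to spare, because power at its own assumed effect size is nearer 80% than the stated 90% (shown below).

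**Working it through.** **Inputs from the documents.** Two to three sites; 1:1 allocation; 50 randomized; 23 per group (46) after dropout; effect size 0.85; two-sided α = 0.05; two-sample t-test; stated power 90% (Sample Size Calculation).

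**Inputs assumed.** Site sizes, and the share *R* of outcome variance explained by site. The documents give neither. *R* is taken at 0%, 5%, 10% and 20%.

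**1. The plan's own power.** With 23 per group and effect size 0.85, the noncentrality is 0.85 × √(23/2) = 2.88 on 44 degrees of freedom, which gives 80.5% power. To reach 90% at 0.85 needs 31 per group by the t-test. The stated 23 per group matches an effect size of 1.00 (91.2% power), a value that the same paragraph also mentions. The starting point for this check is therefore about 80%.

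**2. Chance imbalance within a site.** The text does not say whether the code is simple or restricted, so both are shown.

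| Site size and split | Simple randomization (worst case) | Fixed 25:25 list, no site strata |
|---|---|---|
| 17 subjects, 5:12 or worse | 2·P(Bin(17, ½) ≤ 5) = 14.3% | 2·P(Hyp(50, 25, 17) ≤ 5) = 7.2% |
| 25 subjects, 8:17 or worse | 2·P(Bin(25, ½) ≤ 8) = 10.8% | 2·P(Hyp(50, 25, 25) ≤ 8) = 2.3% |

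Small sites are more exposed. Under the fixed list, a site of 10 splits 3:7 or worse in 29% of cases, and a site of 8 splits 2:6 or worse in 25%.

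**3. How far imbalance moves the estimate.** Take 46 analysed, 23 per arm, no stratification and total SD 1. The chance shift in the treatment difference has SD 2√(*R*/45), which is 0.067, 0.094 and 0.133 at *R* = 5%, 10% and 20%. Multiplying by 1.96 gives about 0.13, 0.18 and 0.26 SD. Simulation (4,000 runs per cell; sites of 23/23, 16/15/15 and 28/10/8) gave 95th percentiles of 0.13–0.14, 0.18–0.19 and 0.25–0.27.

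**4. Type I error of the current plan.** With no stratification and no site term, simulated rejection under no effect was 0.047–0.059, near the nominal 0.05.

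**5. Power with and without the change.** With balanced sites and a site term, the effective effect size is 0.85/√(1 − *R*). The t-test formula ignores the 1–2 degrees of freedom spent on site. Allowing for them changes these figures by about 0.1 point or less.

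| *R* (assumed) | Effective effect size | Power by formula | Simulated: stratified plus site term | Simulated: current plan |
|---|---|---|---|---|
| 0% | 0.850 | 80.5% | 80–81% | 80–82% |
| 5% | 0.872 | 82.4% | 82–83% | 80% |
| 10% | 0.896 | 84.4% | 84–85% | 80–82% |
| 20% | 0.950 | 88.3% | 88–89% | 79–81% |

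Monte Carlo error is about 0.6 point per cell. The simulation analyses a single time point without the baseline covariate, so *R* should be read as the site share left after baseline adjustment.

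**6. One change without the other.** Stratifying by site while leaving site out of the model made the test conservative: type I error was 0.025–0.033 at *R* = 20%. The two changes belong together.

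**The case against.** The strongest reply is that the randomization text is silent rather than explicitly unstratified. A computer-generated 1:1 code could be blocked within site, and Study Product and Mode of Administration refers to a full study protocol. That reference concerns only the tape-tarsorrhaphy, but it shows that a fuller document may exist. This stands: a reader might infer that allocation is known to be simple and to disregard site, and the text does not support that. The model half is firmer, because the terms are listed and site is not one of them.

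Second, protections already exist. Evaluators are masked, the endpoint is change from baseline, and the baseline score is a covariate, so a stable grading offset between sites is partly absorbed. This also stands. It does not cover site differences in response under SOC or in grading drift, and masking does not remove grader-to-grader variance.

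Third, a reader might infer that each site chooses its own SOC. The documents say only that the list is open. If choice varies by patient rather than by site, site may explain little.

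Fourth, the benefit rests wholly on an assumed between-site variance and could be nil. That is correct, and it limits the weight of the point, though the cost of the change is also very small.

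**Conclusion.** The point holds as a modest matter of precision and robustness. Site is absent from the stated allocation method and from the listed model terms. At assumed site shares of 5%, 10% and 20%, stratification plus a site term gains about 2, 4 and 8 points of power by formula (up to about 9 in simulation). At 0% it gains nothing. Without the change, chance imbalance could move the estimate by roughly 0.13 to 0.27 SD at its 95th percentile over the same shares, against an assumed effect of 0.85.

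Two stronger readings should be resisted. The omission does not bias the comparison systematically or inflate type I error, which stayed near 0.05. Nor does it explain why power is about 80% rather than 90%. That gap comes from the sample-size calculation itself and is a separate matter; it only makes avoidable loss of precision less affordable.

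The conclusion rests on the assumed site shares and site sizes, and on the text reviewed being the full statement of the allocation method.

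**What to change.** In Study Subjects and Randomization, state that the code is generated in permuted blocks of varying size within each site, or, if this is already specified elsewhere, say so. In Statistical Methods, add site as a fixed effect to the primary and secondary models, with a pre-specified rule for pooling a very small site.

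If enrolment has begun under another scheme, the site term can still be pre-specified before unmasking.

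The cost is one line in the randomization specification and one model term: 1 degree of freedom with two sites, 2 with three. The only data needed are each subject's site. If site has no effect, there is no gain, or a very slight loss of power (80.5% to 80.4% by the t-test formula with 1 or 2 fewer degrees of freedom).

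### In the text available, random choice of the primary study eye is stated only for the PROKERA arm; no rule is given for the control eye, which is named after allocation

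*Combined protocol and SAP*

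**What the plan says.** - **Study Subjects and Randomization.** The arm comes first: "Subjects will first be randomized in a 1:1 ratio". The eye rule follows and is confined to one arm: "For the PROKERA® Arm, one eye of each subject will be randomly assigned as the primary study eye".
- **Study Population/Duration.** A sentence covering both arms places the choice of eye after allocation: "Following the baseline visit at which the subject will be randomized" to one arm or the other, "one of the two eyes will be designated as the primary study eye". It gives no method and does not say who decides.
- **Study Design.** The study eye is identified only as the eye that receives the device, which cannot define a control eye. Staining is scored in both eyes, starting before treatment: "Signs of corneal epithelial damage will be evaluated by corneal fluorescein staining at the baseline" and at the three monthly visits, with the fellow eye assessed in the same way. On masking: "all evaluators will be masked as to the treatment assignment".
- **Endpoints.** The primary endpoint is the between-arm difference in mean change of the "total corneal fluorescein staining score of the primary study eye from baseline to 1 month". An exploratory outcome repeats the analyses in the fellow eye.
- **Statistical Methods.** The model adjusts for the study eye's own baseline staining score, and the analysis set is described as the randomized eyes in the intent-to-treat population.

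**The concern.** Every control subject has two eyes with baseline scores, and one of them must be named before the primary analysis can be run. If the PROKERA eye is random and the control eye is picked by some other rule, the two arms supply different kinds of eye. An eye picked because it scored low will on average score higher at the next visit, and an eye picked because it scored high will score lower. This regression to the mean would then occur in one arm only and appear as a treatment difference.

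Choosing the better control eye makes controls seem to worsen and raises the chance of a false claim of benefit. Choosing the worse eye makes them seem to improve and costs power. The fellow-eye comparison would show the mirror image, which could be misread as the contralateral effect the study sets out to look for.

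**Working it through.** The plan gives no figure on this point. Its planned standardised effect of 0.85 (Sample Size Calculation) serves only as a yardstick. The documents give no between-eye or visit-to-visit variability, so every SD below is an assumption.

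**Model, no treatment effect.** Score of one eye = subject part (SD *s*) + eye part (SD *e*) + visit noise (SD *v*). Month 1 keeps the first two parts and draws new noise. The PROKERA eye is random; the control eye is always the better one at baseline. The month-1 contrast is approximated by analysis of covariance on the study eye's baseline.

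**Worked example: *s* = 1.0, *e* = 0.8, *v* = 0.75.**

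1. Baseline shift of the chosen control eye: δ = √[(e² + v²)/π] = √(1.2025/3.1416) = 0.619 points lower.
2. Share of that shift that persists: b_D = e²/(e² + v²) = 0.64/1.2025 = 0.532. Unadjusted spurious difference: δ(1 − b_D) = 0.619 × 0.468 = 0.29 points.
3. Baseline slope used for adjustment, pooled over arms:
   - Random arm: covariance s² + e² = 1.64; variance s² + e² + v² = 2.2025.
   - Control arm: with u = (1 − 2/π)(e² + v²)/2 = 0.2185, covariance s² + e²/2 + b_D·u = 1.436; variance s² + (e² + v²)/2 + u = 1.820.
   - b = (1.64 + 1.436)/(2.2025 + 1.820) = 0.765.
4. Bias left after adjustment: (b − b_D)δ = (0.765 − 0.532) × 0.619 = **0.144 points** in favour of PROKERA. The sign reverses if the worse eye is taken.
5. Residual SD = √(2.2025 − 1.64²/2.2025) = 0.991, so the bias is 0.144/0.991 = 0.145 residual SD, and 0.145/0.85 = 17% of the planned effect.

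The covariate halves the bias (0.29 to 0.144) but does not remove it, because b exceeds b_D: at a given baseline score, a chosen better eye tends to have a worse fellow eye, and so a higher expected later score, than a random eye. The fellow eye has the same δ, b_D and b with the shift reversed, so its bias is equal in size and opposite in sign.

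**Range from the same formula.**

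| s, e, v | δ | b_D | b | Bias, points | Residual SD | Bias, residual SD |
|---|---|---|---|---|---|---|
| 1.0, 1.0, 0.5 | 0.631 | 0.80 | 0.8975 | 0.06 | 0.687 | 0.09 |
| 1.0, 0.8, 0.75 | 0.619 | 0.532 | 0.765 | 0.14 | 0.991 | 0.15 |
| 1.5, 0.5, 1.0 | 0.631 | 0.20 | 0.745 | 0.34 | 1.309 | 0.26 |

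**Simulation on the rounded 0–9 scale.** 60 scenarios: mean 3.0–5.0, *s* 1.0–1.2, *e* 0.5–1.0, *v* 0.5–1.0; eligible if either eye scores at least 3; type I error from 20,000 trials of 25 per arm.

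| Control eyes chosen selectively | Adjusted bias, points | Two-sided type I error | False claim of benefit if better eye (nominal 0.025) |
|---|---|---|---|
| None | about 0 | 0.047–0.053 | nominal |
| A quarter | 0.01–0.07 | 0.047–0.057 | 0.029–0.039 |
| Half | 0.03–0.14 | 0.050–0.068 | 0.033–0.055 |
| All | 0.07–0.29 | 0.058–0.124 | 0.046–0.118 |

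The simulated fellow-eye bias is 0.07–0.29 points if all choices are selective and 0.03–0.13 if half are, with the sign reversed. With 23 per arm and a true effect of 0.85 residual SD, simulated power is 0.78–0.81 with random control eyes, 0.67–0.75 if half are the worse eye and 0.52–0.69 if all are. Only the drop from 0.78–0.81 belongs to this point; the shortfall from 90% with random eyes is a separate sample-size matter.

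**The case against.** The case against is substantial.

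- **The rule may exist elsewhere.** The Study Flowchart heading comes directly after the random-eye sentence, and its content is not reproduced. The device-insertion steps also refer to a full study protocol. This stands: the finding is limited to the text available.
- **Designation does not mean discretion.** The sentence covers both arms, and in the PROKERA arm the eye so designated is a random one. This also stands. A reader might infer that control eyes will be picked by judgement, or that the trial is biased; the documents say neither.
- **The analysis section leans the other way.** It speaks of randomized eyes in a population that includes controls. That suggests random control eyes, but it may equally mean the eyes of randomized subjects, and it states no procedure.
- **Evaluators are masked.** Masking protects the scoring. It does not settle who names the control eye, or when.
- **The numbers are assumed, and the largest need an extreme rule.** Agreed. The ranges are not bounds: visit noise of 0.3 gives 0.04–0.12 points, and requiring both eyes to score at least 3 lowers the bias by roughly 10–20%. With a quarter of choices selective, type I error is essentially nominal.
- **Fixing the eye before the arm is revealed goes beyond the gap.** Random choice in both arms would by itself remove the bias. The ordering is an added safeguard against overriding the draw, and it costs nothing.

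**Conclusion.** The point holds as a gap in specification with a possible, not demonstrated, bias. It is more than missing detail: the one stated rule is specific to an arm, and the choice of eye comes after allocation, when both eyes have baseline scores.

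The bias is zero if control eyes are random. In the extreme case where every control eye is the better (or the worse) one, it is roughly 0.06 to 0.34 points after baseline adjustment, about 0.1 to 0.25 residual SD against the planned 0.85. It is about half that if half of the choices are selective, and type I error is close to nominal if a quarter are. The better eye favours PROKERA and the worse eye works against it; the fellow-eye contrast carries a similar bias with the opposite sign. These sizes rest on assumed SDs, normally distributed components and an analysis of covariance standing in for the repeated-measures model. Confidence is moderate, because text not available here may already settle the matter.

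**What to change.** In Study Subjects and Randomization, state that in both arms one eye of each subject is randomly assigned as the primary study eye from the computer-generated list, and that this is fixed before the arm is revealed. Bring the designation sentence in Study Population/Duration, and the statement that the arm is randomized first, into line with this. If the flowchart or the full protocol already gives this rule, align this text with it.

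The cost is one or two sentences and a right/left field in the randomization list. The PROKERA arm's random choice of eye is unchanged, and no visit, assessment or subject is added.

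As a minor separate clarification that adds no weight here, say which eye or eyes the staining criterion of at least 3 applies to.
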